- Absence of at least one minor criteria
- Absence of interobserver agreement between at least 2 surgeons
- More than 1 extension of resection to pancreatic neck due to pancreatic margin positivity

Postoperative

- Wrong randomization

Procedures

Preoperative care

Preoperative care will follow institutional standards, according to each center involved. After obtaining the informed consent for elective pancreatic resection and after adequate counselling, the study will be proposed to the patient. Patients with a main pancreatic duct of the pancreatic neck/body >3mm at preoperative imaging (CT scan or MRI) will be excluded. If the patient will accept, the informed consent will be obtained. The physician who will get the informed consent for the procedure will also be responsible for the consent

to the study. Randomization lists will be provided for each Center and for each randomized group. All patients will be preoperatively checked for diabetes by measuring fasting blood glucose (FBG) and Hb1Ac, C- peptide, and for pancreatic exocrine insufficiency by associated clinical criteria and fecal elastase-1 (FE-1) determination.

Intraoperative setting

The resection phase will be carried out according to clinical practice at each participating center. At the time of pancreatic anastomotic reconstruction, the risk will be calculated on the basis of the presence of major and minor criteria (see Table 1):

- The operating surgeon will assess pancreatic texture by manual palpation (only the distinction between “hard” and “soft” is allowed; the expert pancreatic surgeon manual palpation represents the gold standard for pancreatic texture assessment)¹³
- The operating surgeon will precisely measure the main pancreatic duct caliber in millimeters
- The operating surgeon will assess other risk features related to the pancreatic remnant such as: presence of bleeding, friable or deep pancreatic stump¹⁴; presence of invisible, eccentric or posterior main pancreatic duct; presence of intraoperative pancreatitis; FRS 9 or 10¹
- The operating surgeon will confirm the presumed pathology and estimated blood losses will be assessed in order to calculate the FRS

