The operating surgeon will decide whether the patient can be included in the study or must be excluded for the presence of any drop-out criteria (see above). The interobserver agreement of at least another surgeon will serve as a confirmation for the inclusion in the trial (ethical “guarantor”). According to the presence of two major and one or more minor criteria patients will be included in the study and randomized in two groups. A picture of the pancreatic remnant will be taken intraoperatively before anastomosis/totalization. Both patients undergoing open and minimally invasive surgery can be considered eligible.

PA Group

PA will be carried out according to the techniques adopted by the participating Centre, either pancreaticojejunostomy (PJ) (i.e. dunking PJ, Cattel-Warren duct-to-mucosa PJ, Blumgart PJ) or pancreatico-gastrostomy (PG) will be considered eligible. Any mitigation strategy (i.e. ETS, use of glues/biological matrices to protect the anastomosis, surgical feeding jejunostomy, prophylactic hydrocortisone/somatostatin administration) can be used according to the Center practice. The other two anastomosis, hepaticojejunostomy and duodenojejunostomy (in case of Longmire-Traverso PD) or gastrojejunostomy (in case of Kausch-Whipple PD), will be carried out as usual according to each Institution’s operative standards.¹⁵

At least one surgical drain will be placed in the retroperitoneum in all patients.

TP Group

TP will be carried out according to each Institution’s operative standards. Preservation of the spleen will be considered whenever possible according to Kimura technique. Either ligation or preservation of gastric vessels (right/left gastric artery/vein) will be allowed according to clinical necessity but will be recorded and correlated with postoperative outcomes.¹⁶

The reconstruction phase will be carried out according to each Institution’s operative standards. One or more surgical drains can be left in place according to surgeon’s preference.

Postoperative care

After the procedure, the patient will be admitted to the ICU or in the ward. The management of intravenous fluids, nasogastric tube, bladder catheter and postoperative analgesia will take place as usual according to

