each Institution's standards of care. In the PJ Group, the amylase value of drain fluids will be checked on POD1, POD3 and at any POD if it will help to diagnose a still undiscovered POPF. Surgical drain will be managed according to clinical judgment and each Institution's clinical standards. During hospitalization, all patients will receive specialistic evaluation to assess and possibly treat the occurrence of new onset diabetes or the worsening of pre-existing diabetes. Pancreatic exocrine insufficiency will be treated with oral supplementation of pancreatic enzymes if needed. Patients in the TP Group will be vaccinated 1 month after complete functional recovery against Pneumococcus, Hemophilus influenzae group B, and Meningococcus to minimize the likelihood of developing post-splenectomy sepsis. All patients will receive an outpatient follow-up, 1 month after discharge and every 6 months for 2 years. During follow-up, glycemic control, nutritional status, and possible symptoms of exocrine insufficiency will be assessed, and patients will receive specialistic assistance if needed. QoL will be registered using specific questionnaires. An oncologic evaluation will determine the indication for administration of adjuvant therapy, in case of malignancy.

Questionnaires

All patients who will be alive after at least 12 months of follow-up will be enrolled in the cross-sectional study of quality of life. All the eligible patients who are not able to attend outpatient visits will be contacted by telephone before receiving the 5 questionnaires by mail. Patients who will not respond within 1 month will be contacted again by telephone. Four questionnaires will be administered: (1) the EuroQoL Group questionnaire (EQ-5D); (2) the European Organization for Research and Treatment of Cancer (EORTC) QLQ-C30 questionnaire; (3) the European Organization for Research and Treatment of Cancer (EORTC) QLQ-PAN26 questionnaire; and (4) the Problem Areas in Diabetes (PAID) questionnaire.^{17 18 19 20} The comprehensive assessment will consist of a total of 116 questions.

ENDPOINTS

Primary endpoint

For each study group the primary endpoint is the rate of postoperative major morbidity, defined as Clavien-Dindo ≥ 3 .

Secondary endpoints

For each study group secondary endpoints are:

- Incidence of In-hospital, 30-days and 90-days postoperative mortality. Beyond these time-limits, the mortality that may be related to the operation will be considered and discussed in each case.

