- Respiratory distress (defined as the need for mechanic ventilation after surgery)
- Urinary tract infection
- Neurological morbidity (cerebrovascular accidents, hemorrhage)
- Re-operation
- Re-admission within 30, 60 and 90 days

For PA Group additional secondary endpoints are:

- Incidence and severity of POPF ²⁸
- Incidence of biochemical leak ²⁸
- Overall average complication burden for POPF
- Incidence of postoperative pancreatitis ²⁹

SAMPLE SIZE CALCULATION

A recent metanalysis by Schuh et al. reported a POPF rate around 23% in stage D patients (main pancreatic duct diameter ≤ 3 mm, soft pancreas) but no data were available regarding major morbidity¹². Patients that will be considered eligible for the present trial will have further features increasing their risk of POPF and

related major morbidity, compared to stage D patients. Based on the current literature and on a recent retrospective study by the Verona group, considering only a cohort of patients with extremely high FRS (FRS 9-10), the rate of major morbidity can be estimated around 55% after PD and 19% after TP.¹¹

The original risk score proposed in this trial is extrapolated based on previous literature and expert opinions. For this reason, there are no data directly available for estimation of major morbidity in this rare subset of patients, for which we estimate a rate of Clavien-Dindo ≥ 3 of around 40%.

Considering a 1:1 allocation between the groups, a sample size of 49 patients per group would allow a two-sided, two-sample test for binomial proportions to detect a difference in Clavien-Dindo ≥ 3 of 25% (40% vs 15%) with 80% power ($1-\beta$) and an error α of 0,05. The study has a group sequential design allowing for interim analyses at pre-specified timepoints with possible early stopping for efficacy or futility in case of an overwhelming large or small effect, respectively. Considering that extremely high-risk cases represent around 7% of the total amount of PDs performed and that the fistula risk can only be assessed intraoperatively, we expect to approach preoperatively around 1300 patients.

STATISTICAL ANALYSIS

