Continuous variables will be expressed as the means and standard deviation values or as median values with ranges and will be compared using the Student t-test or the Mann-Whitney test as appropriate. Categorical variables will be analyzed by Chi-square or Fisher's exact test in case of expected small frequencies. All the tests will be 2-tailed. P values < 0.05 will be considered statistically significant. All endpoints will require the above-mentioned statistical analysis, comparing the two study arms. Statistical analyses will be performed using STATA14 for Windows.

DURATION AND END OF THE STUDY

Since the Department of General and Pancreatic Surgery performs about 250 PD per year and the study will be proposed to at least other 2 international referral centers, the primary endpoint will be reached after 25 months: 22 months of patients' enrollment and 3 months of follow-up. Long term analysis of QoL and pancreatic insufficiency will require additional 24 month of follow-up. Time for data analysis must be considered negligible. All the patients undergoing PD will be enrolled for the study if inclusion and exclusion criteria will be respected. The study will be discontinued in case of reaching the statistical significance of the primary endpoint, or in case of suspension by the coordinators or by the authorities.

PROCEDURES RELATED TO REGISTRATION AND DATA MANAGEMENT

To ensure the confidentiality of data, each patient will be registered and de-identified by an identification code.

Each subject will be identified by a code consisting of:

- Code Protocol: TETRIS
- Number of the institution: (e.g. Patient recruited at the Verona Pancreas Institute will be coded as TETRIS_C1)
- Number of recruitment (e.g. the third patient recruited at the Verona Pancreas Institute will be coded as TETRIS_C1_3).

The P.I. of the study will be responsible for data protection and privacy of study participants by treating the data solely for statistical purposes and scientific research, and he will not communicate them if not anonymously. The manager of data processing is the principal investigator.

All data of enrolled patients collected during the study will be recorded in a computerized case report form (CRF) and transferred automatically into a specific database protected by passwords. These data will be kept confidential and will be treated in full compliance with the Legislative Decree 196/03.

ETHICAL CONSIDERATIONS

[figure not shown]

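### Patients are randomised from centre-specific lists, but the primary test ignores centre: a cheap precision improvement, not an error

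*Combined protocol and SAP*

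**What the plan says.** In the combined protocol and SAP, Procedures, Preoperative care: "Randomization lists will be provided for each Center and for each randomized group". Each centre has its own list, so centre is in effect a randomisation stratum. The method of generating the lists and any block size are not given, and the reference to each randomised group is unclear.

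Care also differs by centre:

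- Intraoperative setting: "The resection phase will be carried out according to clinical practice at each participating center".
- PA Group: "PA will be carried out according to the techniques adopted by the participating Centre". Mitigation strategies are likewise left to the centre.
- TP Group: "TP will be carried out according to each Institution" (that is, by its own operative standards).
- Postoperative care: "Surgical drain will be managed according to clinical judgment" and by institutional standards.

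The Statistical Analysis section says "Categorical variables will be analyzed by Chi-square", or by Fisher's exact test where expected frequencies are small, and adds: "All endpoints will require the above-mentioned statistical analysis, comparing the two study arms". The sample size calculation rests on an ordinary two-sided comparison of two proportions. No stratified test, centre covariate or centre-adjusted estimate appears anywhere.

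**The concern.** When allocation is arranged within centre and centres have different event rates, part of the outcome variation is between centres. If the arms are balanced inside each centre, that part cannot contribute to the difference between arms. The crude test still counts it as noise, so its standard error is too large. The test then rejects less often than its nominal 5%, and the interval for the risk difference is wider than it need be.

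The technique of anastomosis, the mitigation strategies, the technique of total pancreatectomy and drain management could all affect Clavien-Dindo ≥ 3, so differences between centres are plausible. With 98 patients and power close to 80%, there is little precision to spare. What is at stake is a little power and interval width, not bias.

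**Working it through.** **1. The plan's own figure.** Inputs from Sample Size Calculation: 40% vs 15%, two-sided α = 0.05, 80% power, 1:1. With the pooled-variance formula and no continuity correction, mean rate 0.275:

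n = [1.96·√(2 × 0.275 × 0.725) + 0.8416·√(0.40 × 0.60 + 0.15 × 0.85)]² / 0.25² = (1.2377 + 0.5102)² / 0.0625 = 48.9, so 49 per group.

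The stated 49 reproduces (power 80.1%). It assumes no stratification.

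**2. Assumptions needed.** The documents give no event rates by centre, no block size and no fixed number of centres (the lead department plus at least two others). The lead centre's share can be approximated from the document: 250 PD per year × 22/12 years = 458, and 458/1300 = 35%, or about 34 of 98. With exactly two other equal centres, the layout is 34/32/32. Assumed spreads in the PA rate are none, 30/40/50% and 20/40/60%, always averaging 40%.

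**3. Size of the crude test, by hand.** Take no treatment effect, perfect balance within centre, 20/40/60%, and 40% in the centre of 34.

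- Variance the crude test uses: 0.40 × 0.60 = 0.24.
- Variance within centres: (34 × 0.24 + 32 × 0.16 + 32 × 0.24)/98 = 0.2139.
- Effective critical value: 1.96/√(0.2139/0.24) = 2.076, a two-sided rejection rate of about 3.8%.

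For 30/40/50% the within-centre variance is 0.2335, the critical value 1.987 and the rejection rate 4.7%.

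**4. Simulation.** 150,000 trials per cell, permuted blocks of 4 or simple randomisation within centre, no continuity correction, single look. Each cell shows crude vs Cochran-Mantel-Haenszel (CMH), in %. Power A takes TP as 0.375 × PA in every centre; power B takes TP as 15% everywhere.

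| Lists | PA spread | Null rejection | Power A | Power B |
|---|---|---|---|---|
| Blocked | none | 5.1 vs 5.2 | 81.0 vs 80.9 | 80.9 vs 80.9 |
| Blocked | 30/40/50 | 4.8 vs 4.9 | 81.2 vs 81.6 | 81.3 vs 81.5 |
| Blocked | 20/40/60 | 3.9 vs 5.0 | 81.9 vs 83.5 | 81.8 vs 82.5 |
| Simple | none | 5.1 vs 5.0 | 80.8 vs 79.5 | 80.9 vs 79.6 |
| Simple | 30/40/50 | 5.2 vs 5.0 | 81.0 vs 80.4 | 81.1 vs 80.1 |
| Simple | 20/40/60 | 5.2 vs 5.0 | 81.0 vs 82.4 | 81.4 vs 81.2 |

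Before rounding, CMH minus crude power runs from about -0.1 to +1.7 points (blocked) and -1.3 to +1.4 (simple). A separate run with a common odds ratio, lists balanced within centre and 20/40/60% gave 80.8 vs 83.1, a gain of 2.3 points, so the gain also depends on how the effect varies across centres.

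**5. Confidence interval.** Half-width of the 95% interval for the risk difference, with 49 per group:

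- Crude: 1.96·√((0.24 + 0.1275)/49) = 17.0 points.
- Stratified, 30/40/50%, TP 15% everywhere: 1.96·√((0.2335 + 0.1275)/49) = 16.8. TP proportional also gives 16.8.
- Stratified, 20/40/60%, TP 15% everywhere: 1.96·√((0.2139 + 0.1275)/49) = 16.4. TP proportional: 1.96·√((0.2139 + 0.1238)/49) = 16.3.

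**6. Other layouts, CMH minus crude power in points (100,000 trials per cell).**

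| Layout | Blocked | Simple |
|---|---|---|
| Three centres, 58/20/20 | 0.0 to +1.0 | -1.3 to +0.4 |
| Eight centres, unpooled | -0.7 to +0.3 | -3.6 to -2.3 |
| Eight centres, those under 12 patients pooled | -0.3 to -0.2 | -0.9 to -0.8 |

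**The case against.** The strongest reply is that nothing is missing. The Statistical Analysis section names an unstratified test for all endpoints, and the sample size is built on the same kind of test, so the two agree and are fixed in advance. That stands: a reader might infer that the plan is silent on how centre enters the analysis, but it specifies a test without centre.

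The second reply is that the benefit rests on blocking and centre differences that the documents do not give. Among the three-centre results in the table, CMH gains more than half a point only under the 20/40/60% spread. With unblocked lists and no spread it loses 1.3 points and falls just below 80%. In the eight-centre layout with pooling it loses in both columns. That layout cannot show a benefit, because the pooled centres average the same 40% as the lead centre. This also stands, and it is why the gain must be described as possibly zero or negative.

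The objection does not make the suggestion mere taste. Analysing by the factor used for allocation keeps the test at its nominal level whether or not the lists are blocked. It gives an interval that matches the design, and it needs no new data.

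**Conclusion.** The point holds as a low-severity improvement. The primary analysis ignores the factor the trial randomises by. Omitting centre does not inflate type I error: rejection under the null is about 5% with unblocked lists, and between 3.9% and 5.1% with blocked lists over the spreads tabulated. The cost, if lists are blocked and centres differ, is a mildly conservative test and an interval up to 0.7 points too wide on each side.

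Three stronger readings are not supported.

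- A reader might infer that the crude test is invalid or the trial underpowered because centre is left out. The calculations show neither, and 49 per group need not change.
- A reader might infer the opposite, that the primary test is sound in every respect. The statement here concerns only the omission of centre, in a single-look, uncorrected Chi-square. The plan also says "The study has a group sequential design allowing for interim analyses at pre-specified timepoints", stops on reaching significance and gives P < 0.05 as its only threshold; that is a separate issue. Fisher's test has 74.5% power at 49 per group, although expected counts at 40% vs 15% are not small enough to call for it.
- A reader might infer that stratifying is sure to gain power. It depends jointly on blocking, centre spread, and the number and size of centres, all of which are assumed here.

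**What to change.** In the Statistical Analysis section, pre-specify for Clavien-Dindo ≥ 3 a Cochran-Mantel-Haenszel test stratified by randomising centre, with the Mantel-Haenszel risk difference and 95% confidence interval. Fix in advance a rule for pooling small centres, for example one stratum for all centres below a set number of randomised patients. Use the same test at any interim look and keep the crude Chi-square as a sensitivity analysis. If the sponsor keeps the crude test as primary, report the Mantel-Haenszel risk difference and interval beside it. A sentence on how the lists are generated would also show which rows of the table apply.

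The cost is two or three sentences and a few lines of Stata code. No new data are needed, since the patient code already carries the institution number. The downside is about 1.3 points of power with three similar centres and unblocked lists. With eight small unpooled centres the loss can reach 0.7 points if blocked or 3.6 if not. Pooling reduces this to about 0.3 and 0.9 points, but gives up any gain where the small centres differ strongly from each other.

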- To evaluate the access to adjuvant chemotherapy (when indicated)
- To evaluate cancer-specific, pancreas-specific, and diabetes-related QoL in each group

MATERIAL AND METHODS

The study will be organized as a multicentric randomized controlled trial. When a patient will be considered eligible preoperatively, he or she will be enrolled in the present study.

The patient's risk will be allocated intraoperatively after the demolitive time and before pancreatic anastomosis, according to the following criteria:

Major Criteria
Main pancreatic duct diameter $\leq 3\text{mm}$
Soft pancreas
Minor Criteria
Bleeding stump
Friable stump
Posterior/Eccentric duct
Invisible duct
Deep pancreas
Intraoperative acute pancreatitis
FRS 9-10
Interobserver agreement
≥ 2 Surgeons

Table 1 Eligible patients will have two major and one or more minor criteria confirmed by at least two surgeons

Patients presenting with all major criteria (stage D according to Schuh et al.¹²) and at least one among the minor criteria will be considered eligible. At least two surgeons must confirm eligibility, according to interobserver agreement regarding the above-mentioned criteria and ethical applicability of randomization (ethical “guarantor”). Eligible patients will be randomized to receive PA or TP.

Pre-operative, intra-operative and post-operative data will be recorded prospectively by the P.I. and by his collaborators.

Population

Inclusion criteria

Preoperative

- Patients older than 18 years
- All patients scheduled for PD for all kind of pancreatic diseases
- Patients able to give their informed consent

Intraoperative

- Patients undergoing PD (Kausch-Whipple or Longmire-Traverso)
- Patients presenting two major and at least one minor criteria (Table 1)
- Two or more surgeons confirming eligibility
- PA or TP with or without spleen preservation (Kimura technique). These techniques are consistent with clinical practice; any other procedure will be a deviation from the protocol

Surgical techniques different from those mentioned in the section “procedures” will be considered as a violation of the current protocol.

Drop-out criteria

Preoperative

- Informed consent withdrawal
- Impossibility to undergo surgery for any reason
- Main pancreatic duct of the pancreatic neck/body >3mm at preoperative imaging (CT scan or MRI)

Intraoperative

- PD not performed for any reason
- Absence of two major criteria

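### The plan's one sentence on operating the randomisation does not stop the next allocation being known or predicted at a centre, while surgeons settle partly subjective eligibility just before allocation

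*Combined protocol and SAP*

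**What the plan says.** Under Procedures, Preoperative care, the plan states: "Randomization lists will be provided for each Center and for each randomized group". Materials and Methods adds only that eligible patients are randomised to pancreatic anastomosis (PA) or total pancreatectomy (TP), and the sample size section gives a 1:1 ratio.

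Eligibility is settled during the operation, after the resection and before the anastomosis. The Intraoperative setting section says: "The operating surgeon will decide whether the patient can be included in the study or must be excluded". It then says: "The interobserver agreement of at least another surgeon will serve as a confirmation for the inclusion in the trial". The criteria are mixed:

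- Judged by hand or eye: "The operating surgeon will assess pancreatic texture by manual palpation", as hard or soft only, and the "presence of bleeding, friable or deep pancreatic stump", for which the text gives no thresholds.
- Measured or calculated: duct calibre in millimetres and the fistula risk score (FRS).
- Discretionary: under Materials and Methods, the two surgeons must also agree on the "ethical applicability of randomization".

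A photograph of the remnant is taken before the anastomosis or completion of the pancreatectomy. The flowchart legend asks for at least two senior surgeons.

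**The concern.** Allocation concealment matters most when those who decide on entry have discretion and may favour one arm. Both conditions apply here. The background reports clearly better postoperative outcomes after TP in the coordinating centre's own series, but also diabetes in every TP patient, so a surgeon could reasonably lean either way for a given patient.

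A surgeon who knows or can guess the next arm can let that knowledge colour a call on softness or friability, or on whether randomisation is ethically applicable. The two arms could then differ in baseline risk, and the comparison of Clavien-Dindo grade 3 or higher would carry that difference.

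The list sentence gives no protection. A list for each group is also hard to read as a single concealed sequence per centre. Even a hidden list can be partly predicted if it uses small fixed blocks, because the surgeons at a centre see every past allocation.

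**Working it through.** **1. The plan's own figure.** Inputs from the sample size section: 40% vs 15%, two-sided alpha 0.05, 80% power, 1:1. With pooled variance and no continuity correction, the mean rate is 0.275 and

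n = [1.96 × √(2 × 0.275 × 0.725) + 0.842 × √(0.40 × 0.60 + 0.15 × 0.85)]² / 0.25² = (1.238 + 0.510)² / 0.0625 ≈ 48.9, so 49 per group.

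Power at 49 is 80.1%. The stated size reproduces, and concealment does not alter it.

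**2. What the text controls.**

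| Step | Stated in the surviving text |
|---|---|
| Who generates the sequence | no |
| Who holds the lists | no; lists are for each centre and each group |
| Block sizes | no |
| Eligibility locked before release | order described (decide, confirm, randomise), but no lock or release mechanism |
| Second surgeon independent or unaware of the list | no |
| Photograph tied to an eligibility review | no |
| Reason recorded when an enrolled patient is not randomised | drop-out reasons are listed; recording is not expressly required |

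**3. Room for unseen selection.** 2 × 49 = 98 randomised from about 1300 approached is 1300/98 ≈ 13 approached per patient randomised. About 1300 − 98 = 1202 would not be randomised, nearly all for legitimate reasons. A few steered cases would not stand out.

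**4. Predictability if centre lists are blocked (illustration; no block size is given).** For a block of four with two per arm, always guessing the arm with more places left gives expected correct guesses of 1/2 + 2/3 + (1/3 × 1 + 2/3 × 1/2) + 1 = 2.83 of 4, or 71%. The fourth allocation is always certain and the third is certain one time in three, so 1.33 of 4, or 33%, are known in advance. The same enumeration gives 75% correct and 50% certain for blocks of two, and 68% and 25% for blocks of six. With a readable list both are 100%.

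**5. Effect on type I error (illustration; no degree of steering is given).** Assume no true difference and 40% risk. Every enrolment is steered: patients entered when PA is expected have risk 40 + s points, and when TP is expected 40 − s. With a proportion q of guesses correct, the spurious arm difference is 2s(2q − 1). For blocks of four and s = 5 this is 2 × 5 × 0.417 = 4.2 points; for a readable list it is 10 points. Two-sided type I error from 200,000 simulated trials, 49 per arm, pooled z-test:

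| Knowledge of next arm | q | s = 2.5 | s = 5 | s = 10 |
|---|---|---|---|---|
| none | 0.50 | 5.0% | 5.0% | 5.0% |
| blocks of 6 | 0.683 | 5.5% | 6.6% | 11.5% |
| blocks of 4 | 0.708 | 5.5% | 7.0% | 13.5% |
| blocks of 2 | 0.75 | 5.8% | 8.0% | 17.3% |
| readable list | 1.00 | 8.0% | 17.2% | 53.0% |

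Steering the other way would hide a true benefit of TP. The table shows only how sensitive the design would be.

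**The case against.** The best defence is that this is missing detail, not a faulty design. Lists provided for a centre may simply be lists stratified by centre and held elsewhere. The plan describes the right order: the surgeon decides, a second surgeon confirms, and the patient is then randomised. The duct is measured, the FRS is calculated and the remnant is photographed. All of this stands as mitigation, but none of it hides the next arm.

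Four stronger readings are tempting, and the documents do not support them.

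- *Surgeons can read the list.* The text does not say so. Foreseeability is a risk left open, not a shown breach. The flowchart figure and some pages are also not available to check.
- *Declining a patient leaves no trace.* Patients consent and are enrolled before surgery, receive a sequential code and enter the computerised case report form, and failing the intraoperative criteria is a listed drop-out category. Hard to detect is the most that can be said.
- *The bias can be sized from the plan's own rates.* One might treat the assumed 40% as a mixture of 55% (FRS 9-10) and 31% (the rest). Then 0.55x + 0.31(1 − x) = 0.40 gives x = 0.375. Withholding half of the FRS 9-10 cases from PA would give a rate of (0.1875 × 0.55 + 0.625 × 0.31)/0.8125 = 36.5%, and withholding all of them 31%. But 31% is the rate for the whole high-risk series, which probably already includes FRS 9-10. The 37.5% share appears nowhere, and the 40% is an estimate for a differently defined population. The withholding shares are arbitrary. These figures are pure illustration.
- *No analysis could repair it.* Imbalance in a recorded item such as the FRS can be examined and adjusted for. Imbalance in features that are not recorded cannot.

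**Conclusion.** The point holds as a gap in protection. The plan's one operating sentence does not prevent the next allocation from being known or predicted at the centre, and entry rests partly on surgeons' judgement moments before allocation. That leaves the primary comparison open to selection bias, in either direction, which would be hard to detect.

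No size can be attached from the documents. The type I error figures depend on assumed block sizes, an assumed degree of steering and steering of every enrolment; they range from almost no inflation to severe. The conclusion rests on the surviving text being complete on this matter. If a concealed central system already exists, the remedy is only to describe it.

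**What to change.** Replace the list sentence with a statement to this effect: one concealed 1:1 sequence per centre, generated with randomly varying block sizes not disclosed to sites, is held centrally. The allocation is released through the electronic case report form, or a web or telephone system, only after both surgeons have entered the major and minor criteria, including their judgement that randomisation is applicable, and locked eligibility. No list is held at a centre.

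Add a requirement to record the reason for every enrolled patient who is not randomised, by centre, so that selective non-randomisation can be looked for.

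The cost is setting up a randomisation module alongside the computerised case report form already planned, and a short delay in theatre while the criteria are entered. The sample size, endpoints and surgical procedures are unaffected. This is a cheap improvement.
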